Patients with neuropsychological diagnoses are reported to be more likely to develop severe COVID-19 disease. Previous work has shown an increased incidence of severe respiratory infection and worse critical care outcomes associated with pharmacological neuropsychological treatments. It remains unclear whether particular conditions or treatments predispose to severe COVID-19 disease (requiring hospital, critical care admission or death) more than to other acute respiratory infections. Patients with COVID-19 disease are reported to subsequently have a high incidence of neuropsychological disease. However, the incidence of neuropsychological sequelae is also high following other critical illness. It is unclear whether neuropsychological sequelae following severe COVID-19 disease are more serious or managed differently than following other severe acute respiratory infection (SARI) such as bacterial or viral pneumonia, particularly when accounting for risk factors associated with the disease.

Antecedent analysis

We will explore the associations between pharmacological treatments (hypnotics and anxiolytic, antidepressant, drugs used in psychoses and related disorders) of preexisting neuropsychological diagnoses (anxiety, mood, psychotic disorders, or dementia), and severe clinical outcomes of COVID-19 infection (hospital admission, ICU admission and death) in comparison to those not receiving such treatments.

We will determine whether the associations between pre-existing neuropsychological treatments and severe clinical outcomes differ for patients with COVID-19 infection in comparison to patients with non-COVID-19 severe acute respiratory infections (SARI)

Sequelae analysis

We will determine the risks of receiving a new neuropsychological diagnosis or new neuropsychological medication within one year after discharge from hospital for patients admitted with COVID-19 infection in comparison to patients with non-COVID-19 severe acute respiratory infections (SARI) investigating the subgroups of hospitalised patients admitted to and not admitted to an ICU.

INTRODUCTION

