This study will investigate neuropsychological disease and treatments before and after severe COVID-19 disease. The two main aims are:

1. to evaluate the associations of pre-existing neuropsychological diseases and treatments with severe COVID-19 outcomes in comparison to patients without pre-existing neuropsychological pathology;

2. to evaluate the associations between hospital or ICU admission due to COVID-19 and neuropsychological sequelae following discharge home in comparison to patients with ICU admission due to non-COVID-19 severe acute respiratory infections (SARI).

Objectives

- 1. To assess whether pre-existing neuropsychological diseases (by separate diseases and overall) are associated with severe COVID-19 outcomes (hospital and ICU admission and death) in comparison to the general population.
- 2. To assess whether pre-existing neuropsychological treatments (as a class and individually where possible) are associated with severe COVID-19 outcomes (hospital and ICU admission and death) and whether these explain disease associations in comparison to those not receiving such treatments.
- 3. To assess whether the risk of severe COVID-19 outcomes with prior neuropsychological disease differs from the risk of severe outcomes with SARI.

After discharge following a hospital admission for COVID -19 infection:

- 4. To assess the incidence of new neuropsychological diseases up to one year after hospital and ICU discharge following treatment for COVID-19 disease.
- 5. To compare the incidence of new neuropsychological diseases up to one year after hospital and ICU discharge with COVID-19 disease to the incidence following discharge after treatment for SARI.

Summary of the potential impact

This study will provide a better understanding of how pre-existing psychopathology and concomitant medication affect the risk of hospital and ICU admission and death due to COVID-19 and how any differences between those with and without preexisting psychopathology and COVID-19 infection compare to other severe acute respiratory infections. We will discover the neuropsychological sequelae of admission to a hospital or ICU with COVID -19 disease, taking into account prior neuropsychological disease and whether these differ from patients discharged from an ICU following SARI. These findings will be key to prevention and management of ongoing problems for these patients.

METHODS

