 Cohort one is adult patients aged 18 years of age or over on 24th January 2020 (the study entry date, when the first confirmed COVID-19 case occurred in the UK) who were registered in a primary care practice within the QResearch programme on or before 24th January 2019. Patients will be followed-up from study entry date until development of severe COVID-19 disease, defined as the first date of either hospitalisation, ICU admission, or death. Patients will be censored at the first occurrence of deregistration from the GP practise, death, or date of the final data extract from the linked datasets.

Cohort two is an open cohort of patients aged 18 years of age or over (including those who become 18 within this period) who had been registered with a primary care practise within the QResearch database for at least one year, between 24th January 2015 and 23rd January 2020. For each patient, the earliest day on which all these conditions were met will be defined as their study entry date, and they will be followed-up until development of severe disease due to SARI, defined as hospitalization, ICU admission, or death. Patients will be censored at the earliest of first occurrence of deregistration from the GP practise, death from other causes, 24th January 2020 or date of the final data extract from the linked datasets.

Aim 2.

- Cohort three will include adult patients (aged 18+ on date of hospital admission) discharged alive following a hospital admission including an ICU admission resulting from COVID -19 infection (defined below) between 24 January 2020 and study end date, who were registered in a primary care practice within the QResearch programme before their ICU admission. It will be used to evaluate the risk of subsequent neuropsychological sequalae from the date of discharge. Patients will be censored at the earliest of first occurrence of deregistration from the GP practice, death from other causes, 12 months post discharge from hospital, or date of the final data extract from the linked datasets.

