For cohort two, our primary outcome is the first occurrence of either hospital admission with SARI in the HES dataset (defined as a new ICD-10 code J09-J22 in the HES dataset) or ICU admission in the ICNARC CMP dataset with SARI (defined as any admission with unique diagnostic code any one of RE129 RE131 RE82 RE50 RE86 RE94 RE75 RE133 RE132 RE121 RE1 RE128 RE16 RE130 RE117 RE42 RE41) or death. Secondary outcomes will be each of these three events considered separately (I.e. SARI related hospital admission, ICU admission, death).

Aim 2.

Our primary outcome is development of new neuropsychological disease up to 1 year following hospital discharge which we define as having received a diagnostic code as below:

- Anxiety and stress-related disorders [ICD F40-48 and corresponding Read codes]
- Mood disorders [ICD F30-39 and corresponding Read codes]
- Psychotic disorders [ICD F20-29 and corresponding Read codes]
- Dementia [ICD F00-F03, G30, G31.0 ? and corresponding Read codes]

Secondary outcomes are the diagnosis of new neuropsychological disorders (as defined above) with treatment, and where numbers are available the new diagnosis with or without treatment of each class of disorders, each considered as a separate endpoint.

Neuropsychological treatments are defined as:

- Hypnotics and anxiolytics: (hypnotics, anxiolytics, barbiturates and methyprylone, benzodiazepines)
- Antidepressant drugs (Tricyclic and related antidepressant drugs, Monoamine-oxidase inhibitors, Selective serotonin re-uptake inhibitors, Other antidepressant drugs)
- Drugs used in psychoses and related disorders (Antipsychotic drugs and depot injections, Lithium salts, Phenothiazine derivatives)

Definition of exposures

Aim 1

Neuropsychological disease will be defined as an ordinal variable with the following three categories: no relevant diagnosis or drugs; diagnosis ever recorded without recent drug treatment; diagnosis present with recent drug treatment (with at least two prescriptions for neuropsychological treatments as above within the six months preceding study entry).

Our primary exposure is active neuropsychological disease on the study entry date which we define as having received a diagnostic code as above (24th January 2020 for cohort 1 and 24th January 2015 for cohort 2).

Aim 2.

The primary exposure is a hospital or ICU admission resulting from COVID-19 infection. Comparator exposures are hospital or ICU admission resulting from SARI.

Covariates

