Cause-specific Royston Parmar flexible parametric models will be used to estimate the hazard ratios of developing new neuropsychological diseases after having received intensive care, comparing patients who received intensive care for COVID-19 (cohort 3) vs those who received intensive care for SARI (cohort 4). This model will adjust for all previously listed covariates. The age variable will be included as a restricted cubic spline rather than a linear term. Follow-up will start on the date of discharge from hospital.

Proportional hazards assumption will be tested, and time dependent terms will be included if the hazard ratio changes over time. A random frailty term will be included to account for similarities amongst patients admitted in the same critical care unit

A limited number of two-way interactions which are considered to be clinically or biologically plausible will be identified prior to analysis, and tested using a Wald test.

Primary care data on some potential confounding variables is incomplete (e.g. smoking status, alcohol intake, ethnic group, BMI). Reason for admission is mandatory for all records in the ICNARC database (the core dataset for aim 2), so classification of these reasons as either SARI or COVID related will be non-missing for all patients. Only admission records for completed critical care stay (non-missing length of stay and survival status at end of critical care) will be included (n.b. outcomes are missing in <1% of COVID ICU admissions to date). Remaining variables from the critical care stay are use of sedation in the first 24 hours, and duration of advanced respiratory support, which are missing for a small number of patients (<1.5%).

Both aims.

To allow data analysis with all eligible patients, we will impute missing data in all cohorts. We will use multiple imputation with chained equations under the missing at random assumption to replace missing values and use these values in our main analyses [15]. We will include all exposure and confounding variables in the imputation model, along with the Nelson–Aalen estimator of the baseline cumulative hazard, and the outcome indicator. We will carry out five imputations. Analysis models will be fitted in each imputed dataset and Rubin's rules to will be used to combine the results across the imputed datasets.

As the analyses are on time to event data, patients will be censored at the date when they are lost to follow-up as defined in cohort definitions above.

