
Figure 1: Data flow diagram for cohort 1 and cohort 2 for the antecedent study.

Figure 2: Data flow diagram for cohort 3 and cohort 4 for the antecedent study.

AIM 2 - sequelae study

COHORT 2

- age 18+ at hospital/ICU admission
- pandemic period: 24/01/20 XX
- COVID-19 ICU DISCHARGED PATIENTS (ICNARC)
- N = XX
- COVID-19 HOSP DISCHARGED PATIENTS (HES)

N = XX

ALL DEATHS (ONS) N = XX

\rightarrow QRESEARCH N = XX

- COVID-19 ICU DISCHARGED PATIENTS
- (ICNARC) n = XX COVID-19 HOSP DISCHARGED PATIENTS (HES) n = XX
- ALL DEATHS (ONS) n = XX

COHORT 3

- (to be used as compartor for COHORT 2)
- age 18+ at hospital/ICU admission
- historical cohort: 24/01/15 23/01/20
- SARI ICU DISCHARGED PATIENTS

(ICNARC)

- N = XX SARI HOSP DISCHARGED PATIENTS (HES) N = XX
- ALL DEATHS (ONS) N = XX

→ QRESEARCH N = XX

- SARI ICU DISCHARGED PATIENTS (ICNARC) n = XX
 SARI HOSP DISCHARGED PATIENTS
- (HES) n = XX
- ALL DEATHS (ONS) n = XX

Figure 3. Directed Acyclic Graph for Aim 1.

Figure 4. Directed Acyclic Graph for Aim 2.

Version history

Version	date	author	Notes
1.0	27.11.2020	PST, MP, RH, PW, CC	
1.2	12.12.2020	PST	Updated after teams meeting 11.12.20
1.3	22.03.2021	PW	
1.4	25.06.2021	PW,MP,CC,KT,DH	
1.5	23.07.2021	a/a	TR made final changes

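### The opening summary promises a COVID-19 versus SARI comparison in hospitalised patients who never entered an ICU, but every post-discharge cohort requires an ICU stay, so that comparison has no eligible patients

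*Protocol*

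**What the plan says.** **What is announced.** The Sequelae analysis paragraph of the opening summary compares COVID-19 with SARI after hospital discharge, "investigating the subgroups of hospitalised patients admitted to and not admitted to an ICU". Under Definition of exposures, Aim 2, the protocol states: "The primary exposure is a hospital or ICU admission resulting from COVID-19 infection". It then adds: "Comparator exposures are hospital or ICU admission resulting from SARI". Objective 5 concerns the "incidence of new neuropsychological diseases up to one year after hospital and ICU discharge with COVID-19 disease", compared with SARI. The flow diagram for the sequelae study has an entry for "COVID-19 HOSP DISCHARGED PATIENTS (HES") beside the ICU discharges, and a matching entry for SARI.

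**What is specified.** Under Participants, Aim 2, cohort 3 consists of adults "discharged alive following a hospital admission including an ICU admission resulting from COVID -19 infection (defined below"). Cohorts 4 (SARI, 2015 to 2020) and 5 (SARI, from 24 January 2020) carry the same condition. All three cohorts also require patients to be "registered in a primary care practice within the QResearch programme before their ICU admission". Statistical Methods, Aim 2, compares intensive care patients in cohort 3 with intensive care patients in cohort 4, and adds: "A random frailty term will be included to account for similarities amongst patients admitted in the same critical care unit".

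**The concern.** The population in the question and the population in the cohort definitions differ. A patient treated for COVID-19 or SARI on a ward only, and discharged alive, falls within the exposure definition and within a subgroup named in the summary, yet cannot enter any cohort that is followed after discharge.

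Two things are at stake. One half of the announced subgroup comparison cannot be estimated. In addition, two analysts working from this document could extract different Aim 2 populations, one following the exposure definition and the other the cohort definitions. The choice of population should be fixed before the extract is made.

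**Working it through.** No formula applies. The Aim 2 sizes are expected counts given without a derivation, so there is no figure to reproduce. The check sets the relevant sections side by side.

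| Section of the protocol | Aim 2 population it implies |
|---|---|
| Opening summary, Sequelae analysis | Hospitalised, with ICU and non-ICU subgroups |
| Aims, item 2 | COVID-19: hospital or ICU. SARI: ICU only |
| Objectives 4 and 5 | Hospital and ICU discharge |
| Summary of the potential impact | COVID-19: hospital or ICU. SARI: ICU only |
| Definition of exposures, Aim 2 | Hospital or ICU, both diseases |
| Participants, cohorts 3, 4 and 5 | Hospital stay that includes an ICU stay |
| Effect Modifiers, Aim 2 | Intensive care admission |
| Study Size, Aim 2 | ICU admissions in the ICNARC database |
| Statistical Methods, Aim 2 | Intensive care patients, with ICNARC as the core dataset |
| Sensitivity analyses, propensity score | Patients admitted to critical care |
| Flow diagram, sequelae study | ICU discharges (ICNARC) and hospital discharges (HES) |

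**Step 1: can a ward-only patient enter cohorts 3 to 5?** The eligibility wording could be read loosely, as hospital stays with ICU stays among them. Four points rule that out:
- The registration condition is timed to the patient's own ICU admission, so it presupposes one for every member.
- Study Size draws Aim 2 from ICNARC ICU admissions only.
- Statistical Methods accepts only records of a completed critical care stay.
- The model compares only patients who received intensive care.

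On the strict reading, the number of members without an ICU stay is 0 in cohort 3, 0 in cohort 4 and 0 in cohort 5.

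**Step 2: can another cohort supply them?** No. Cohorts 1 and 2 serve Aim 1, and their follow-up ends at the severe outcome. They are not followed from discharge.

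**Step 3: could the Aim 2 model accept ward-only patients if they were added?** Not as specified. The frailty term is the critical care unit, which a ward patient does not have. Statistical Methods adjusts for all listed covariates. Under Intensive care stay these include length of stay, duration of advanced respiratory support and sedation in the first 24 hours, which are not defined for a ward patient.

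**Step 4: do the stated sizes cover them?** No. The expected numbers are about 11,000 admissions for cohort 3, 7,000 per year for cohort 4 (5 × 7,000 = 35,000 over its five years) and 3,500 for cohort 5. All follow from the sentence that limits Aim 2 to ICU admissions. No figure is given for ward-only patients.

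**The case against.** The strongest reply is that Aim 2 is in substance an ICU study whose front matter was not kept in step. The cohort definitions, Bias, Study Size, Statistical Methods, propensity analysis and Discussion are all framed on ICU patients, and the Introduction also describes the comparison as one of patients treated on an ICU. On that view one announced subgroup lacks a cohort, and deleting a few phrases would settle it. Much of this stands, and it is why the second repair below is a legitimate choice.

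The supporting evidence should also not be overstated. A reader might infer that the second aim, the objectives, the exposure and the diagram all promise a non-ICU subgroup. They do not:
- Only the opening summary names patients not admitted to an ICU.
- The second aim and the impact summary set hospital or ICU COVID-19 patients against SARI patients from ICU only.
- Objectives 4 and 5 join hospital and ICU discharge with *and*, which ICU survivors satisfy.
- The flow diagram labels the sequelae cohorts 2 and 3 and shows no cohort 5. That does not match the numbering in the text, so the diagram is weak evidence of present intent.

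The objection does not remove the contradiction between the summary and exposure definition on one side and the cohort definitions on the other. An analysis plan not seen here could add detail on ward patients, but the protocol's eligibility text would still exclude them.

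**Conclusion.** The inconsistency is real. The COVID-19 versus SARI comparison in hospitalised patients without an ICU stay has zero eligible patients in cohorts 3, 4 and 5. This rests on the strict reading of the cohort definitions, which the registration condition, data source and model all support. The protocol does not itself state the zero.

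Two stronger conclusions are tempting, and the document supports neither. The first is that the ICU hazard ratio is biased or cannot be estimated. The ICU contrast is coherently defined and is untouched by this defect. The second is that findings in ICU survivors will be reported as applying to all hospitalised patients. The Discussion promises sequelae results only for patients admitted to an ICU, so that would be conjecture about reporting.

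**What to change.** Choose one of two repairs before the Aim 2 cohorts are extracted.

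**(a) Bring ward patients in.**
- Define cohorts 3 to 5 as adults discharged alive after a COVID-19 or SARI hospital admission. Use the outcome definitions already given for Aim 1: HES with PHE test results for COVID-19, and HES codes for SARI.
- Require practice registration before the hospital admission, and flag ICU admission yes or no from ICNARC.
- Fit the COVID-19 versus SARI model separately in the ICU and non-ICU strata. A single pooled model would meet covariates that ward patients cannot have.
- Keep the critical-care-unit frailty and the ICU-stay covariates in the ICU stratum only. In the non-ICU stratum use GP practice or hospital as the cluster.
- Restate the expected sizes by stratum, and amend the statement that ICNARC is the core dataset.

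The cost is a larger extract and some added model specification. HES and PHE are already linked and the outcomes come from QResearch, so no new data source is needed.

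**(b) Restrict the question to ICU survivors.** Amend the opening summary, the second aim, objectives 4 and 5, the Aim 2 exposure and comparator, and the flow diagram, so that all refer to patients discharged after an ICU stay. The cost is a narrower conclusion, with nothing said about patients treated on wards alone.

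Under either choice, align the second aim and the impact summary so that the COVID-19 and SARI sides describe the same kind of admission, and renumber the cohorts in the diagram.

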Sensitivity analyses

We will undertake complete case analysis in those without missing data as a sensitivity analysis of our findings.

We will also restrict analysis to only include patients with confirmed COVID-19 diagnosis using RNA testing.

For Aim 2 we will carry out a sensitivity analysis in cohort four with additional censoring of follow-up on 24th January 2020, so that outcomes are assessed prior to the pandemic period. In comparing cohort 3 and 4 we will consider the competing risk of death by undertaking a competing risk analysis.

In order to compensate for the low expected event rates relative to our sample sizes for aim 2, we will combine cohorts 3 and 4 and use all available baseline characteristics (as listed previously) to calculate a propensity score to measure the likelihood of developing a new neuropsychological condition up to 1 year after ICU admission. We will then use these scores (with inverse probability weighting) to compare the adjusted hazard of developing a new neuropsychological condition in patients admitted to critical care for COVID compared to those admitted for SARI.

The authors will have full access to anonymised data from the Case Mix Programme, QResearch and Public Health England, and Hospital Episode statistics databases. We will remove duplicate records for the same individual, and set dates and values outside a pre-defined credible range as missing. For patients admitted with SARI between 2015-2020 the full set of standard data validation processes for unit level data intended for public reporting will have been carried out by ICNARC. Some of the more recent Covid admissions will have undergone a more restricted set of validations, but these do include confirming the total number of admission with Covid to each unit, checking that duration of organ support does not exceed duration of stay, and confirming with units that that aggregated units level summaries of length of stay and organ support (among other measures) are in line with expectations. All variables used in the analysis will be initially summarised in a table of baseline characteristics to include minimum, maximum, median and quartiles.

Data linkage

Person-level data linkage will be undertaken between QResearch, Hospital Episode Statistics, the Case Mix Programme and Public Health England. Cases will be matched on pseudonymised NHS number [15].

Discussion

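### Aim 2 promises one-year risks but plans no main analysis that allows for death, and the censoring rule for cohorts 3 to 5 names only deaths from other causes

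*Protocol*

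**What the plan says.** The protocol sets absolute quantities as targets for Aim 2. Its opening summary (Sequelae analysis) states: "We will determine the risks of receiving a new neuropsychological diagnosis or new neuropsychological medication within one year after discharge from hospital". Objective 4 reads: "To assess the incidence of new neuropsychological diseases up to one year after hospital and ICU discharge following treatment for COVID-19 disease". Objective 5 begins: "To compare the incidence of new neuropsychological diseases up to one year after hospital and ICU discharge with COVID-19 disease", with SARI as the comparator.

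Under Definition of outcomes, Aim 2, the endpoint is a diagnostic code alone: "Our primary outcome is development of new neuropsychological disease up to 1 year following hospital discharge". Death is not part of it.

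Under Participants, Aim 2, follow-up of cohort three ends at the earliest of deregistration, "death from other causes, 12 months post discharge from hospital, or date of the final data extract from the linked datasets". Cohorts four and five carry the same rule. Statistical Methods (Both aims) refers back to it: "patients will be censored at the date when they are lost to follow-up as defined in cohort definitions above".

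The main analysis under Statistical Methods, Aim 2 is: "Cause-specific Royston Parmar flexible parametric models will be used to estimate the hazard ratios of developing new neuropsychological diseases", for cohort 3 against cohort 4. Death as a competing event appears once, under Sensitivity analyses: "In comparing cohort 3 and 4 we will consider the competing risk of death by undertaking a competing risk analysis".

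**The concern.** There are two separate gaps.

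**No main analysis yields the promised risk.** A cause-specific hazard ratio compares rates of diagnosis among people still alive and undiagnosed. It is not a one-year risk, and Objective 4 concerns a single cohort, so no ratio can answer it. If a one-year risk were read off the death-censored model as one minus its survival function, patients who had died would be treated as still able to be diagnosed. The planned competing-risk analysis would avoid this, but it is limited to cohort 3 versus 4. It leaves out the Objective 4 incidence. It also leaves out cohort 5, which the Bias section adds so that COVID-19 and SARI survivors can be compared over the same calendar period.

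**The censoring rule does not fit the outcome.** Limiting censoring to deaths from other causes makes sense for cohort two, where death belongs to the endpoint. In cohorts 3 to 5 no death is an event, so the qualifier has nothing to refer to. As written, a death from COVID-19 or SARI after discharge is neither an event nor an end of follow-up.

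At stake are the absolute risks that the study says it will report. Under a literal reading of the censoring rule, the person-time behind the hazard ratio is affected too.

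**Working it through.** The protocol states no event count, incidence or mortality for Aim 2, so there is no figure to reproduce. The inputs below are assumptions that illustrate direction and size.

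**Inputs (assumed)**
- Net one-year risk of diagnosis, p: 5% or 10%. Sensitivity analyses describes Aim 2 event rates as low but gives no figure.
- One-year mortality after discharge, q: 5%, 10% or 20%.
- Constant hazards over the year: l = -ln(1 - p) for diagnosis and d = -ln(1 - q) for death.

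**Check 1: risk with deaths censored against cumulative incidence**

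With deaths censored, the risk is 1 - exp(-l) = p. With death competing, the cumulative incidence is CIF = l/(l + d) × (1 - exp(-(l + d))).

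Example with p = 10% and q = 20%: l = 0.1054, d = 0.2231 and exp(-(l + d)) = 0.90 × 0.80 = 0.72. So CIF = 0.1054/0.3285 × 0.28 = 8.98%, an excess of 1.02 points.

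| Net risk p | Mortality q | CIF | Excess of p over CIF (points) |
|---|---|---|---|
| 10% | 5% | 9.75% | 0.25 |
| 10% | 10% | 9.50% | 0.50 |
| 10% | 20% | 8.98% | 1.02 |
| 5% | 5% | 4.88% | 0.12 |
| 5% | 10% | 4.75% | 0.25 |
| 5% | 20% | 4.49% | 0.51 |

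The relative excess is about 2.5%, 5% and 11% at 5%, 10% and 20% mortality, and hardly depends on p.

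**Check 2: equal diagnosis hazards, unequal mortality**

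Take p = 10% in both groups, with mortality of 10% in one and 20% in the other. The cause-specific hazard ratio is 1.00 and the death-censored risks have ratio 1.00. The cumulative incidences are 9.50% and 8.98%, a ratio of 1.058. The rate comparison and the risk comparison are therefore different questions.

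**Check 3: the literal censoring rule**

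Suppose every death is due to the index infection and those patients stay at risk until 12 months. Write s = l + d.
- Events: l/s × (1 - exp(-s)).
- Correct person-time: (1 - exp(-s))/s.
- Person-time wrongly added after death: d × [1/s - (1 - exp(-s))/s²].

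With p = 10% and q = 10%: events 0.0950, correct person-time 0.9017 and added person-time 0.0492. The apparent rate is 0.0950/0.9508 = 0.0999, against a true 0.1054, a ratio of 0.95. At 5% and 20% mortality the ratios are 0.97 and 0.90. This error runs downward, opposite to Check 1.

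**Check 4: where deaths come from**

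Three places in the protocol differ. Data linkage lists Office of National Statistics COVID-19 mortality. Data sources takes mortality from HES. The sequelae flow diagram lists all ONS deaths. The first alone would not give all-cause death after a SARI discharge, so an any-cause rule needs this settled.

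**The case against.** The strongest reply is that the protocol nowhere plans to read a one-year probability from one minus a Kaplan-Meier or net survival curve. It plans hazard ratios, and for a cause-specific model censoring at death is the standard treatment. Incidence in Objective 4 could mean a person-time rate, for which censoring at death is also right, and the text elsewhere uses risk loosely for hazard. The competing-risk analysis covers the one Aim 2 comparison that Statistical Methods actually models. The choice of a descriptive estimator could sit in a statistical analysis plan that is not at hand.

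Much of this stands. A reader might infer that the study's one-year incidence is overstated, and most so in the cohort with higher mortality. The document does not support that. The overstatement depends on an estimator it does not name, and it gives no mortality for any cohort. Nor does the other-causes wording support it, since taken literally that wording lowers the rate. It would also be wrong to express the excess in multiples of a standard error: the rates are assumed, and the expected numbers under Study Size are largely counts of admissions, whereas the analysis concerns patients discharged alive.

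Two things are left. The censoring phrase is wrong on its face for cohorts 3 to 5, and Statistical Methods refers back to it without repair. And the protocol itself fixes the competing-risk analysis as a sensitivity check for cohort 3 versus 4, while its summary commits to determining risks within one year.

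**Conclusion.** The point holds as a mismatch between the promised quantity and the planned analysis, plus a censoring rule that does not fit the outcome. The cause-specific hazard ratio, with all deaths censored, is sound and should stay; under the usual independence assumption, a difference in mortality alone does not bias it.

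If a one-year risk were taken from the death-censored model, it would be too high by about 0.25 to 1.0 points at a 10% net risk, and by about half that at 5%, for one-year mortality of 5% to 20%. If deaths from the index infection were left at risk, the event rate would be 0.97 to 0.90 of its true value over the same mortality range (at a 10% net risk). Both ranges rest on assumed rates and constant hazards. The second also assumes that every death is due to the index infection. Which cohort would be more affected cannot be determined from the protocol. The wording defect needs no assumed figures.

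**What to change.** 1. In the definitions of cohorts 3, 4 and 5, censor at death from any cause instead of death from other causes. State one source for all-cause death after discharge, reconciling Data linkage, Data sources and the sequelae flow diagram.
2. Keep the cause-specific hazard ratio as the main comparison. As the one-year risk for Objectives 4 and 5, report the 12-month cumulative incidence with death as a competing event in each of cohorts 3, 4 and 5. Use the Aalen-Johansen estimator, or paired cause-specific Royston-Parmar models for diagnosis and death.
3. Extend the competing-risk analysis under Sensitivity analyses to cohort 3 versus 5.

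The cost is a wording change, one additional model for death, and reported risks slightly lower than a death-censored curve would show. Whether further mortality data are needed depends on which of the three stated sources is actually linked.
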